4.2 Secondary Endpoints

Study endpoints related to the secondary efficacy objective:

[figure not shown]

Study endpoints related to the safety objective:

[figure not shown]
- 1. All adverse events (AE) will be graded according to the National Cancer Institute's Common Terminology for Adverse Events (NCI CTCAE, Version 5.0)
- 2. Serious adverse events (SAEs)

Confidential Page 12 of 37

- 3. AE attribution of relatedness to tozuleristide and/or Canvas system (related vs. unrelated)
- 4. Laboratory parameters
- 5. Electrocardiogram (ECG) parameters
- 6. Vital signs

[figure not shown]

Confidential Page 13 of 37

Confidential Page 14 of 37

STATISTICAL HYPOTHESES AND CRITERIA OF SIGNIFICANCE

Approximately 114 subjects are planned for treatment in this study.

Page 15 of 37 Confidential

7 ANALYSIS POPULATIONS

[figure not shown]
The full analysis population (FAP) for efficacy analyses will consist of all subjects who

[figure not shown]
Confidential Page 16 of 37

- 1. meet all eligibility criteria,
- 2. undergo neurosurgery, and
- 3. have central pathology tumor assessment and imaging operator fluorescence assessment of equivocal tissue specimens obtained from the first neurosurgery on study.

Subjects in the FAP will be classified into 4 groups:

- Group 1 (Arm 1): subjects who do not receive tozuleristide, regardless of fluorescence outcomes and tumor diagnosis
- Group 2 (Arm 2 Fluorescent): subjects who receive tozuleristide, have at least one fluorescence-positive study tissue specimens of any type (primary, equivocal, and other) based on imaging operator fluorescence assessment, and the subject's central pathology consensus diagnosis is tumor, ambiguous, or not definitive

The FAP will be the primary analysis population for all efficacy analyses, summaries, and listings.

The safety analysis population (SAF) will consist of all subjects who receive any amount of tozuleristide or receive neurosurgery prior to any re-treatment. The SAF will be used for all safety data summaries and listings.

Confidential Page 17 of 37

The all-subject population (ASP) is defined as all subjects who sign informed consent. The ASP will be used for screen failure summaries and listings.

The intent-to-treat (ITT) population is defined as all subjects who are randomized. The ITT population will be used for disposition summaries, protocol deviations, and listings.

No subjects will be excluded from any analysis populations due to protocol deviations.

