#### 3.3 Inclusion Criteria

Subjects must meet all of the following criteria to be included in this study:

- 1. Subjects must be >1 month and  $\leq 30$  years of age at the time of study enrollment
- 2. Subjects must have MRI obtained within 30 days of study enrollment documenting a measurable lesion consistent with a pediatric primary CNS tumor for which maximal safe resection is indicated
- 3. Adequate renal function defined as:
  - a. Serum creatinine within normal limits for age or calculated creatinine clearance ≥75 mL/min/1.73 m² based on Schwartz equation or normal creatinine for age based on the following table:

Age	Maximum Serum	
	Creatinine (mg/dL)	
	Male	Female
1 to < 2 years	0.6	0.6
2 to < 6 years	0.8	0.8
6 to < 10 years	1	1
10 to < 13 years	1.2	1.2
13 to < 16 years	1.5	1.4
≥ 16 years	1.7	1.4

4. Adequate liver function defined as:

- a. Bilirubin <2 x upper limit of normal
- b. Alanine aminotransferase (ALT)  $\leq$  3 x upper limit of normal
- c. Serum albumin >2 g/dL

5. Prior therapy: Subjects with prior therapy are eligible provided they have recovered from any acute toxic effects of prior therapy and have sufficient time interval prior to enrollment:

- a. Radiation therapy: subjects may not have had radiation therapy to the area of tumor planned to be resected within 28 days of study enrollment
- b. Chemotherapy: at least 14 days from any myelosuppressive chemotherapy (28 days if prior nitrosourea) and if prior chemotherapy, must have an absolute neutrophil count recovery of ≥ 1000/mm^3 following count nadir
- c. Biologic: at least seven days from any anti-neoplastic biologic agent (at least three half-lives since last administration of monoclonal antibodies)
- d. Immunotherapy: at least 42 days after completion of any cellular immunotherapy, such as CAR-T cell therapy
- e. Prior surgery for CNS tumors is allowed
- f. Prior tozuleristide: at least one week after prior dose of tozuleristide if previously treated. NOTE: Subjects previously enrolled on PNOC012 study and randomized to either Arm 1 (control) or Arm 2 (treatment) will be eligible for re-enrollment for open-label treatment of tozuleristide (re-treatment) in the event another surger(ies) is clinically indicated (Section 4.1.3).

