## 10.2.5 Analyses of Primary Efficacy Endpoints

The primary efficacy analyses will be based on Group 2 in the full analysis population (Section 10.2.2). The four sets of statistical hypotheses will be evaluated by assessing the statistical significance of the co-primary endpoints.

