4 STUDY ENDPOINTS

4.1 Primary Efficacy Endpoints

[figure not shown]
The primary efficacy endpoints are:

- 1. Ratio of sensitivity of tozuleristide fluorescence in equivocal tissue biopsies from subjects with fluorescence-positive tumors compared to the sensitivity of surgical designation from the same biopsies under white light conditions
- 2. Ratio of specificity of tozuleristide fluorescence in equivocal tissue biopsies from subjects with fluorescence-positive tumors compared to the specificity of surgical designation from the same biopsies under white light conditions
- 3. Sensitivity of tozuleristide fluorescence to detect tumor in equivocal tissue biopsies from subjects with fluorescence-positive tumor
- 4. Specificity of tozuleristide fluorescence to detect tumor in equivocal tissue biopsies from subjects with fluorescence-positive tumor

Fluorescence positivity for the primary endpoints is defined as weak or strong fluorescence as determined by the imaging operator fluorescence assessment based on displayed fluorescence signal and exposure setting.

Confidential Page 11 of 37

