8.11.1 Primary Efficacy Endpoints

8.11.1.1 Primary Analyses of Sensitivity and Specificity

The primary efficacy analyses will be based on Group 2 in the full analysis population (Section 7). Each of the 4 sets of statistical hypotheses will be tested at two-sided 5% level (Section 5) using the repeated measures log-linear model specified in this section. Each equivocal tissue specimen from Group 2 that is determined to be either tumor positive or tumor negative by central pathology, and has an image operator assessment and/or a surgeon assessment will be used in the analysis.

[figure not shown]
Confidential Page 22 of 37

[figure not shown]
Confidential Page 23 of 37

[figure not shown]
Confidential Page 24 of 37

Confidential Page 25 of 37

Confidential Page 26 of 37

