13.2 Definition of Tumor Diagnosis

Subjects are eligible for enrollment based on MRI evidence consistent with a pediatric primary CNS tumor. Study specimens are subjected to pathological analysis and along with local pathology assessments, a diagnosis is assigned by Central Pathology. Tumor diagnosis is based on WHO Classification of Tumors of the Central Nervous System, 4th Edition, 2016. Subjects with ambiguous pathological diagnosis of tumor or no definitive pathological diagnosis are considered to have a pediatric primary CNS tumor. Subjects with a pathological diagnosis indicative of non-tumorous abnormality are considered to not have a pediatric primary CNS tumor.

[figure not shown]

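### Does leaving dosed non-tumour subjects out of Group 2 make the primary specificity unsound?

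*SAP*

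**What the plan says.** - **Who is enrolled.** Protocol 3.3 asks for an MRI "documenting a measurable lesion consistent with a pediatric primary CNS tumor for which maximal safe resection is indicated". SAP 13.2 agrees: "Subjects are eligible for enrollment based on MRI evidence consistent with a pediatric primary CNS tumor". Histology is not required, and the drug is given before surgery.
- **Who counts as non-tumour.** SAP 13.2: "Subjects with a pathological diagnosis indicative of non-tumorous abnormality are considered to not have a pediatric primary CNS tumor". Ambiguous and non-definitive diagnoses are counted as tumour.
- **Group 2.** SAP 7, matched by Protocol 10.2.2, requires that subjects receive tozuleristide, that they "have at least one fluorescence-positive study tissue specimens of any type (primary, equivocal, and other) based on imaging operator fluorescence assessment", and that "the subject's central pathology consensus diagnosis is tumor, ambiguous, or not definitive".
- **What is analysed.** Protocol 10.2.5: "The primary efficacy analyses will be based on Group 2 in the full analysis population". SAP 8.11.1.1 makes the unit of analysis "Each equivocal tissue specimen from Group 2 that is determined to be either tumor positive or tumor negative by central pathology", given an operator and/or surgeon assessment.
- **What is claimed.** Endpoint 4 in SAP 4.1 is "Specificity of tozuleristide fluorescence to detect tumor in equivocal tissue biopsies from subjects with fluorescence-positive tumor". Endpoints 1 to 3 carry the same restriction. The primary objectives (Protocol 1.1, SAP 2.1) concern subjects undergoing resection of pediatric primary CNS tumours.
- **What cannot be read.** The full analysis population (FAP) has four groups, but only Groups 1 and 2 are legible. The hypotheses, the secondary efficacy endpoints and most of SAP 8.11 are not shown either.

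**The concern.** Specificity is measured on tumour-negative tissue, and the diagnosis condition removes the subjects whose tissue should all be tumour-negative. Such subjects carry extra weight. A tumour subject adds only the tumour-negative share of its equivocal biopsies to the denominator, while a non-tumour subject adds all of them.

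The condition also uses the final central diagnosis, which in many subjects is unknown when the operator reads the image. A surgeon working on an MRI-selected lesion cannot tell whether the patient belongs to the population that endpoint 4 describes. Group 1, by contrast, is kept whatever the diagnosis.

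If non-tumour lesions fluoresce more often than tumour-negative tissue in tumour subjects, endpoint 4 would look better than specificity over everyone dosed. If they fluoresce less often, it would look worse. Endpoint 2 could move either way, because the same biopsies also leave the surgeon's specificity.

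**Working it through.** **The one figure that can be reproduced.** 1:10 allocation of 114 subjects gives 114/11 = 10.4 and 114 × 10/11 = 103.6, in line with about 10 and 104 in Protocol 4.1.1. No power, specificity threshold or biopsy count is legible, so the total of 114 cannot be re-derived.

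**Assumptions.** Only the 104 comes from the documents. The rest is assumed: all 104 evaluable; three specimens per subject (one primary, two equivocal); 35% of equivocal specimens tumour-negative in tumour subjects; specificity 0.750 there; K dosed non-tumour subjects; the same false-positive rate q for every specimen in them.

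**Weight of the excluded subjects.** Their share of all tumour-negative equivocal biopsies is K / (K + (104 − K) × s), where s is the tumour-negative share in tumour subjects. For K = 5 (4.8% of 104):
- s = 0.1: 5/14.9 = 33.6%
- s = 0.35: 5/39.65 = 12.6%
- s = 0.5: 5/54.5 = 9.2%

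**Two comparisons that must be kept apart, at K = 8.** Tumour subjects supply 96 × 2 × 0.35 = 67.2 tumour-negative specimens, of which 0.75 × 67.2 = 50.4 are true negatives. Non-tumour subjects have 8 × 2 = 16 equivocal specimens.

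*A. Drop the diagnosis condition, keep the fluorescence condition.* A non-tumour subject enters only if one of three specimens fluoresces, with probability p = 1 − (1 − q)³. The specimens added are 16p, of which 16(p − q) are true negatives. Specificity = (50.4 + 16(p − q)) / (67.2 + 16p).

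*B. Add all dosed non-tumour subjects, fluorescent or not.* Specificity = (50.4 + 16(1 − q)) / (67.2 + 16).

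| q | p | A | 0.750 − A, points | B | 0.750 − B, points |
|---|---|---|---|---|---|
| 0.10 | 0.271 | 0.743 | +0.7 | 0.779 | −2.9 |
| 0.25 | 0.578 | 0.728 | +2.2 | 0.750 | 0.0 |
| 0.40 | 0.784 | 0.709 | +4.1 | 0.721 | +2.9 |
| 0.60 | 0.936 | 0.679 | +7.1 | 0.683 | +6.7 |

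Column A isolates the diagnosis condition. Column B mixes in the fluorescence condition: at q = 0.10, 0.9³ = 73% of non-tumour subjects have no fluorescent specimen and would be outside Group 2 anyway. The negative entry in B therefore does not come from the diagnosis condition. Deleting that condition alone would not help either. At q = 0.25 in every subject it gives 0.728 where the all-dosed value is 0.750, because it admits only non-tumour subjects selected for fluorescing.

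**The baseline.** 0.750 describes all tumour subjects, not Group 2. If primary fluorescence and sensitivity are both 0.80 and the false-positive rate is 0.25, the chance that one of a subject's other two specimens fluoresces is 1 − 0.20 × (1 − (0.65 × 0.80 + 0.35 × 0.25)) = 0.9215. Group 2 specificity is then 0.75 × 0.9215 / (0.25 + 0.75 × 0.9215) = 0.734. The table shows scale only.

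**Endpoint 2.** Take K = 5, q = 0.40, all dosed subjects, and surgeon specificity 0.60 in tumour subjects. There are 99 × 2 × 0.35 = 69.3 tumour-negative specimens from tumour subjects and 10 from the others. Fluorescence specificity is (0.75 × 69.3 + 10 × 0.60)/79.3 = 0.731. The starting ratio is 0.75/0.60 = 1.25.
- Surgeon specificity 0.30 in non-tumour subjects: (0.60 × 69.3 + 3)/79.3 = 0.562, ratio 1.30.
- Surgeon specificity 0.80 in them: (0.60 × 69.3 + 8)/79.3 = 0.625, ratio 1.17.

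**The case for a change.** The strongest case for a change is that the tool is meant to aid decisions in patients chosen by MRI, so specificity ought to describe those patients. An all-dosed estimate would use data the FAP already requires, and writing it down before database lock would keep it from being labelled post hoc.

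Part of this stands. The restriction is real, the excluded biopsies weigh more than a head count suggests, and a reader should not carry endpoint 4 over to everyone with a suspicious MRI. An all-dosed estimate, split by diagnosis and shown with the number of non-tumour subjects, would be a reasonable optional addition.

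It does not show a fault. The endpoint never claims the wider population. Limiting the specificity claim to fluorescence-positive tumour, which is the safeguard one would ask for, is already its wording. Only definite non-tumour diagnoses leave. Prior CNS surgery is allowed (Protocol 3.3), so in some subjects histology may be known beforehand. Entry to the FAP does not depend on diagnosis, and SAP 7 uses the FAP for all efficacy summaries and listings, so these subjects are not lost from the record. Dosed FAP subjects outside Group 2 presumably fall in Groups 3 and 4, which cannot be read, so it cannot be said that no analysis of them is planned.

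**Conclusion.** The reading of the plan is correct: tumour-negative equivocal biopsies from dosed subjects with a definite non-tumour diagnosis do not enter endpoints 2 and 4. It is a declared choice of target population, carried consistently through the objectives, the endpoints and Group 2, and it gives a sound answer for that population. No change is needed.

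The cost is generalisability. For endpoint 4, the diagnosis condition alone is worth about 0.7 to 7 points upward with 8 non-tumour subjects and false-positive rates of 0.10 to 0.60, and nothing if no such subject occurs. Against all dosed subjects the difference runs from −2.9 to +6.7 points, but that comparison also contains the fluorescence condition. The direction for endpoint 2 is undetermined. Every input except the 104 dosed subjects is assumed, so these figures show scale and do not predict the result.

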8 PLANNED METHODS OF ANALYSIS

8.1 Overall Plan

In general, descriptive statistics will be provided for all the study endpoints and will be presented in tables and/or graphs. Continuous variables will be summarized using the number of observations (n), mean, median, standard deviation, minimum and maximum. Categorical variables will be summarized with frequency counts and percentages. Percentages will be rounded to one decimal place, with the denominator being the number of subjects in the relevant population (N), unless otherwise stated.

Statistical tests will be performed at either a one-sided significance level of 2.5% or a two-sided significance level of 5%. All confidence intervals (CIs) will be constructed at a two-sided 95% confidence level.

In addition, data collected after re-treatment will be listed and will not be included in the primary efficacy and safety analyses.

8.2 Key Definitions

Study Day is the day relative to the date of neurosurgery, where Day 1 is the day of the first neurosurgery performed in this study.

Study Day will be calculated using the first neurosurgery date as the reference date. If the date of interest occurs on or after the first neurosurgery date, study day will be calculated as (date of interest – first neurosurgery date) + 1. If the date of interest occurs prior to the first neurosurgery date, study day will be calculated as (date of interest – first neurosurgery date). There will be no study Day 0.

Unless otherwise specified, the baseline value for a measurement used in all statistical analyses will be the most recent non-missing measurement prior to the administration of the study drug for Arm 2 and prior to the first neurosurgery for Arm 1.

A change from baseline value is calculated as the post-baseline value minus the baseline value.

Confidential Page 18 of 37

Treatment-emergent adverse event (TEAE) is defined as an adverse event that is newly occurring or worsens following neurosurgery (Arm 1) or treatment with tozuleristide (Arm 2).

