#### 4.1.1 Treatment Allocation

After enrollment, subjects will be randomized 1:10 to Arm 1 (no drug treatment) or Arm 2 (tozuleristide treatment).

Arm 1: Approximately ten subjects (~9% of subjects) will not receive tozuleristide and will undergo standard of care neurosurgery.

[figure not shown]
Arm 2: Approximately 104 subjects (~91% of subjects) will receive tozuleristide at a dose of 15 mg/m^2 administered as a single IV bolus dose at least one hour and no more than 36 hours before the planned start time of surgery.

Re-treatment arm: See Section 4.1.3 below regarding re-treatment.

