#### 7 ADVERSE EVENTS

An AE or adverse experience is any untoward medical occurrence in a subject who is administered an investigational product (whether it is the experimental product or the control) and which does not necessarily have a causal relationship with the investigational product. An AE can therefore be any unfavorable and unintended sign, symptom, or disease temporally associated with the use of a medicinal product, whether or not considered related to the medicinal product. Pre-existing events that increase in frequency or severity or change in nature during or as a consequence of use of a drug in human clinical trials, will also be considered as AEs. AEs may also include pre- or post-treatment complications that occur as a result of protocol-mandated procedures (e.g., invasive procedures such as biopsies).

For investigational medical devices, adverse events are any untoward medical occurrence, unintended disease or injury, or untoward clinical signs (including an abnormal laboratory finding) in subjects, users or other persons, whether or not related to the investigational medical device. An adverse device effect is an adverse event related to the use of the investigational medical device. It can include adverse events from insufficient or inadequate instructions for use, deployment, implantation, installation or operation, or any malfunction of the investigational device.

Any medical condition or laboratory abnormality with an onset date before randomization is considered pre-existing and should be recorded on the medical history CRF page(s).

AEs will be collected from time of randomization through three months after surgery or until start of other tumor-directed therapy, whichever is earlier. After the Day 8 visit, all subjects will be followed by chart review and/or telephone contact if no patient visit is documented every month for three months, or until start of other tumor-directed therapy (chemotherapy, radiation therapy or other investigational therapy), whichever is sooner.

If the patient experiences an AE considered to be related to study products, then the patient will be followed until resolution of that AE or until they are off study (whichever is earlier). An AE does not include:

- Medical or surgical procedures (e.g., surgery, endoscopy, tooth extraction, transfusion); the condition that leads to the procedure is an AE
- Pre-existing diseases or conditions present or detected prior to randomization that do not worsen

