#### 10.2.8.1 Adverse Events

Adverse events will be coded using MedDRA 21.0. Adverse events will be defined as treatment-emergent if they are newly occurring or worsen following surgery (Arm 1) or treatment with tozuleristide (Arm 2 and re-treatment). Adverse events will be scored for severity using NCI CTCAE version 5.0 if applicable, or the protocol specified severity stated in Section 7.1.

All adverse events (AEs) and SAEs collected during the study will be graded according to the National Cancer Institute's Common Terminology for Adverse Events (NCI CTCAE, Version 5.0) along with attribution of relatedness to tozuleristide and/or Canvas system and neurosurgery (related vs. unrelated).

Treatment-emergent AEs, SAEs, severity of AEs, tozuleristide-related AEs, Canvas-related AEs, neurosurgical-related AEs, and AEs leading to withdrawal from study will be summarized by MedDRA preferred term and system organ class. In the event of multiple occurrences of the same AE with the same preferred term in the same subject, the AE will be counted once at the greatest severity/relatedness.

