8.12.2 Adverse Events

Adverse events will be summarized by the system organ class (SOC) and preferred term (PT) based on the MedDRA dictionary. The actual version will be documented in the CSR.

Adverse events will be defined as treatment-emergent if they are newly occurring or worsen following neurosurgery (Arm 1) or treatment with tozuleristide (Arm 2). Adverse events with incomplete start dates will be considered treatment emergent if:

- Day and month are missing and the year is equal to or after the year of the first neurosurgery for Arm 1 or the first dose date for Arm 2;
- Day is missing and the year is after the year of the first neurosurgery for Arm 1 or the first dose date for Arm 2;
- Day is missing and the year is equal to the year of the first neurosurgery for Arm 1 or the first dose date for Arm 2 and the month is equal to or after the month of the first neurosurgery for Arm 1 or the first dose date for Arm 2;
- Year is missing; or
- Start date is completely missing.

However, if the end date of the AE is before the first neurosurgery for Arm 1 or the first dose date for Arm 2, this AE will not be treatment emergent regardless of the completeness of its start date.

Adverse events will be graded using the NCI CTCAE, version 5.0 if applicable, or the protocol specified severity stated in Section 7.1 of the protocol.

Treatment-emergent AEs, SAEs, severity of AEs, tozuleristide-related AEs, Canvas-related AEs, neurosurgical-related AEs and AEs leading to withdrawal from the study will be summarized by MedDRA preferred term, system organ class and treatment arm for the safety analysis population. In the event of multiple occurrences of the same AE with the same preferred term in the same subject, the AE will be counted once at the greatest severity/relatedness.

The summaries presenting frequency of AEs by SOC and PT will be ordered by overall descending frequency of SOC and then, within a SOC, by overall descending frequency of PT for Arm 2.

Confidential Page 28 of 37

Only the TEAEs from Arm 1 and Arm 2 will be included in the summary tables. All AEs will be included in the listings. Additional listings will be provided for SAEs, AEs leading to death and AEs leading to study withdrawal.

In addition, treatment-emergent AEs for the re-treatment period are defined as newly occurring or worsen following the open-label treatment of tozuleristide. All AEs reported during the re-treatment period will be listed.

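### New events between dosing and surgery are tabulated in Arm 2 but not in Arm 1, and whether Arm 1 onset during surgery counts is undefined

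*SAP*

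**What the plan says.** - **Definition.** SAP 8.2 counts as treatment-emergent an "adverse event that is newly occurring or worsens following neurosurgery (Arm 1) or treatment with tozuleristide (Arm 2". SAP 8.12.2 repeats this. Protocol 10.2.8.1 has the same anchors: "newly occurring or worsen following surgery (Arm 1) or treatment with tozuleristide (Arm 2 and re-treatment".
- **Timing of the dose.** Under protocol 4.1.1, tozuleristide in Arm 2 is "administered as a single IV bolus dose at least one hour and no more than 36 hours before the planned start time of surgery".
- **Collection.** Protocol 7 applies one rule to both arms: "AEs will be collected from time of randomization through three months after surgery or until start of other tumor-directed therapy, whichever is earlier".
- **Display.** SAP 8.12.2 summarizes TEAEs, SAEs, severity, and drug-, Canvas- and neurosurgery-related AEs by treatment arm. It adds: "Only the TEAEs from Arm 1 and Arm 2 will be included in the summary tables". Other events are not lost: "All AEs will be included in the listings".
- **Neighboring rules.** The Arm 1 baseline is the last value before first neurosurgery (SAP 8.2). An incomplete Arm 1 start date counts if it falls in or after the month or year of surgery, and an event that ended before surgery is excluded (SAP 8.12.2). A medication is concomitant if taken on the date of first neurosurgery or later (SAP 8.12.6).

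**The concern.** Safety is a secondary objective and Arm 1 is the only randomized group without the drug, so readers will set the two columns of the AE tables side by side. The columns do not cover the same period. Arm 2 includes the hours after the dose and before the operation, with whatever pre-operative care falls in them; Arm 1 does not. If the event rate in those hours were the same in both arms, the tables would still show more events in Arm 2, purely through the definition.

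The plan also leaves open whether an Arm 1 event that begins during the operation is treatment-emergent. In Arm 2 such an event always is, because the dose came first.

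**Working it through.** **1. Arm sizes (protocol 3.2 and 4.1.1).** With 114 subjects at 1:10, Arm 1 has 114 × 1/11 = 10.4 and Arm 2 has 114 × 10/11 = 103.6. This reproduces the plan's figures of about 10 and 104.

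**2. What each column counts, for a new event with a complete date and time.**

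| Onset | Arm 1 tables | Arm 2 tables |
|---|---|---|
| After randomization, before the dose (Arm 1: earlier pre-operative period) | No | No |
| Dose to start of surgery (Arm 1: same hours before surgery) | No, unless it worsens following surgery | Yes |
| During the operation | Not defined | Yes |
| After the operation | Yes | Yes |

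The difference that the text settles is the second row only. The third row depends on what *following* neurosurgery means.

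**3. Reading the third row.** Three rules point to the start or date of surgery as the Arm 1 anchor: the pre-surgery baseline, the incomplete-date rule that includes the month or year of surgery, and the end-date rule that excludes only events over before surgery. Two things leave it open:
- SAP 8.12.6 states an inclusive date rule for medications, and the AE definition does not.
- SAP 8.12.2 has no rule for a complete start date on the day of surgery.

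In addition, with the day missing, an Arm 1 event in the month of surgery counts even if it was pre-operative. An incomplete date can thus be treated more inclusively than a complete one.

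**4. Length of the extra Arm 2 window.** Take three months as about 91 days: 91 × 24 = 2,184 h. The share of the Arm 2 window is extra / (2,184 + extra).
- Arm 1 anchored at the start of surgery: 1/2,185 = 0.05% to 36/2,220 = 1.6%.
- Arm 1 anchored at the end of surgery, with an assumed operating time of 2 to 10 h: 3/2,187 = 0.14% to 46/2,230 = 2.1%.

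**5. Illustration with assumed risks.** Let p be the risk per subject, equal in both arms, of a new event in the unequal window that does not later worsen. For a single preferred term, let q be the post-surgery risk, independent of p. Arm 2 then tabulates 1 − (1 − p)(1 − q) and Arm 1 tabulates q.

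| p | Arm 2 subjects tabulated, 104p | Arm 1 subjects affected, 10p (tabulated: 0) | Chance that at least one Arm 1 subject is left out, 1 − (1 − p)^10 | Arm 2 vs Arm 1, q = 10% | Arm 2 vs Arm 1, q = 30% |
|---|---|---|---|---|---|
| 5% | 5.2 | 0.5 | 40% | 14.5% vs 10% | 33.5% vs 30% |
| 10% | 10.4 | 1.0 | 65% | 19% vs 10% | 37% vs 30% |
| 20% | 20.8 | 2.0 | 89% | 28% vs 10% | 44% vs 30% |

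The apparent excess is p(1 − q). It shrinks as q rises, because a subject is counted once per preferred term. The larger values of p are more plausible if the operation itself falls in the unequal window. The documents give no AE rate and no operating time, so none of these rows is a prediction.

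**The case against.** Starting treatment emergence at the dose is the natural choice for drug safety, since it captures acute post-dose events. All AEs are listed, and each is attributed separately to drug, device and surgery (protocol 7.1). No between-arm AE test is shown. The stated purpose of the 1:10 allocation is to limit selection bias and the expectation of fluorescence and to protect the blinded reads (protocol abstract and 4.1.2). It is not to give a safety control of about ten subjects. The extra window is also short. SAP 8.4 assigns drug administration to Day 1, and SAP 8.12.4 puts the pre-dose and pre-surgery vital signs on Day 1. If anchors are applied by date and dosing is on the day of surgery, the gap largely disappears.

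Most of this stands, and it limits the consequence to an uneven description. It does not remove the unevenness. Listings do not correct a table, attribution is a judgment made event by event, and dosing may fall on an earlier calendar date.

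A reader might go further and infer that Arm 1 intraoperative events drop out of the tables, so that the Canvas- and neurosurgery-related tables are distorted as well. The documents do not support this. It requires *following* neurosurgery to mean after the operation ends; no text says so, and the rules in step 3 point the other way. Canvas is used only after the tumor has been reached (protocol abstract, SAP 3.1). The Canvas-related table is therefore affected only if onset during surgery is excluded, and the neurosurgery-related table mainly so.

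**Conclusion.** The point holds in a limited form. A new event between dosing and surgery enters the Arm 2 tables, while its Arm 1 counterpart appears only in listings unless it worsens after surgery. Whether Arm 1 onset during surgery counts is an undefined term to settle, not a demonstrated exclusion. If it were read as excluded, intraoperative and acute Canvas-related events would leave the Arm 1 tables too.

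The size of the bias is unknown. The figures in step 5 rest on assumed, equal risks in both arms and on anchors applied by time rather than by date. A reader might take some fixed percentage-point excess from them, but the documents supply no rate to support one. With about ten controls, moving one subject shifts Arm 1 incidence by about 10 points, so even a small omission shows in the table. No error rate or decision rule is affected. The change is worth making because it is cheap.

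**What to change.** 1. For every between-arm AE table, use one window in both arms: onset or worsening on or after the start of first neurosurgery, including the operation. If the onset time is missing, use the date of surgery.
2. Add one table of pre-surgery events: Arm 2 from dose to surgery, beside Arm 1 over a comparable interval, for example the 36 hours before surgery.
3. Keep the dose-anchored TEAE table as the Arm 2 drug-safety display.
4. State in SAP 8.2, SAP 8.12.2 and protocol 10.2.8.1 that onset during surgery counts in Arm 1, and add a rule for complete start dates on the day of surgery. Rewording the Arm 1 phrase alone is not enough, because the Arm 2 anchor would stay at the dose.

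The cost is wording in three places and one extra table. AEs are already collected from randomization in both arms. Protocol 7.1 records onset time only where possible, so the date-level fallback in item 1 is needed.
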